### **8.1. Analysis of Primary Efficacy Endpoint**

Not applicable.

### **8.2. Analysis of Secondary Efficacy Endpoints**

Not applicable.

### **8.3. Safety Analyses**

*Summaries will include data for all subjects who took at least one dose of study medication in this study (Safety population).*

*The safety data (including adverse events, clinical laboratory assessments, ECGs, vital signs, height/weight, and physical/neurological examinations) will be summarized through standard data tabulations, descriptive statistics, and/or graphical presentations.*

The 3-tier safety analysis approach will not be utilized as this is not a comparative study.

### **8.3.1. Treatment and Disposition of Subjects**

Subject evaluation groups will show subject disposition and number of subjects analyzed for safety (adverse events and laboratory data). Frequency counts will be supplied for subject discontinuation(s)

Data will be reported in accordance with the sponsor reporting standards.

### **8.3.2. Demographic Data and Clinical Examination Data**

A breakdown of demographic data will be provided for age, race, weight and height. Each will be summarized by sex at birth.

### **8.3.3. Discontinuation**

#### **8.3.4. Subject discontinuations, temporary discontinuations or dose reductions due to adverse events will be summarized.**

### **8.3.5. Adverse Events**

AEs will be reported in accordance with the sponsor reporting standards, including frequency and severity.

### **8.3.6. Seizure Frequency**

*Twenty-eight-day seizure rate will be calculated from the seizure diaries and will be reviewed as a means of determining seizure control. Seizure frequency for each seizure type will be summarized using descriptive statistics by visit until the end of the trial by treatment group and overall. No statistical inferences will be performed. PGTC and POS seizure types will be summarized separately.*

**PGTC Seizure Frequency:** will be summarized for subjects from study A0081105 with primary diagnosis of PGTC, and age range from 5 to 65 years. Baseline 28-day seizure rates for PGTC subjects will be the diary data collected prior to initiating double-blind dosing study A0081105. Other than baseline, time points are relative to study A0081106 open-label treatment phase. The 28-day PGTC seizure rate during treatment phase will be reported descriptively for each visit in study A0081106 and overall and will be also reported by age cohorts (5 to 16 years,  $\geq 17$  years). For other types of seizure which are not part of the 28-day PGTC rate (ie, myoclonic, absence seizure, tonic/tonic, clonic, unclassified, status epilepticus) percent of subjects who experienced at least one myoclonic, absence seizure, tonic/tonic, clonic, unclassified, status epilepticus will be summarized.

**POS Seizure Frequency:** will be summarized for subjects from study A0081041, A0081042 and from direct enrollers with primary diagnosis of POS, and age range from 1 month to 16 years. Baseline is not represented for POS subjects as only a subset of these subjects (those from Study A0081041) had seizure diary observations prior to the initiation of study treatment. Baseline seizure data were collected using V-EEG for subjects previously in Study A0081042, which are not comparable to seizure data collected in Study A0081106 using diaries. Direct enrollers into Study A0081106 did not have observation of seizures prior to initiation of study treatment.

The 28-day POS seizure rate during treatment phase will be reported descriptively for each visit in study A0081106 and overall. For other types of seizure which are not part of the 28-day POS rate (ie, unclassified, status epileptic) percent of subjects who experienced at least one unclassified, status epileptic will be summarized.

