## 7.5. Seizure Counts

Subjects, parents or guardians will be responsible for completing a daily seizure diary throughout the subjects' study participation. The diary will enumerate the number of seizures experienced each day, and the seizure type for each seizure event.

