### **9.4. Safety Analysis**

Summaries will include data for all subjects who took at least one dose of study medication in this study (Safety population).

The safety data (including adverse events, clinical laboratory assessments, ECGs, vital signs, height/weight/Tanner stage, suicidality assessments, cognitive assessments, and physical/neurological examinations) will be summarized by treatment group and overall through standard data tabulations, descriptive statistics, and/or graphical presentations.

Twenty-eight-day seizure rate will be calculated from the seizure diaries and will be reviewed as a means of determining seizure control. Seizure frequency for each seizure type will be summarized using descriptive statistics every 4 weeks thereafter until the end of the study by treatment group and overall. No statistical inferences will be performed.

Subgroup analysis will be done on the safety data and seizures rates for each age cohort and primary seizure type.

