### 6.2.3. Seizure Frequency

The seizure frequency for PGTC and POS seizure will be based on the 28-day seizure rate at each visit and overall (all treatment days during the treatment phase, excluding the taper phase), calculated as follows:

$$\text{28 day seizure rate} = \frac{\text{\# of seizures since last visit}}{[\text{\# of days since last visit} - \text{\# of missing diary days since last visit}]} \times 28$$

- Number of days since last visit is defined as: Date of last diary data entry since last visit – Date of first diary data entry since last visit +1.

Calculations will be made, using A0081106 visit schedule, for Week 1 (Visit 2), Month 1 (Visit 3), Month 2 (Visit 4), Month 4 (Visit 5), Month 6 (Visit 6), Month 9 (Visit 7), Month 12 (Visit 8) and Overall.

The 28-day seizure rate for all POS will be computed for subjects from Studies A0081042, A0081041, and direct enrollers, for each visit in study A0081106 and overall. Since these subjects were all <17 years of age at the time of entry to the previous studies, there will be only one age cohort.

The 28-day seizure rate for PGTC seizures will be computed for subjects from Study A0081105 for each visit in Study A0081106 and overall. The 28-day PGTC seizure rate will also be summarized by age cohort (5 to 16 years and  $\geq 17$  years).

Number and percent of subjects who experienced at least one unclassified epileptic seizure, status epilepticus, myoclonic, absence seizure, tonic/tonic & clonic seizure will be computed for all subjects for each visit in study A0081106 by primary seizure type cohorts (PGTC, POS). These seizure types are not part of the PGTC or POS 28-day seizure rate.

The following specifications in regard to the handling of special cases for the seizure diary are also considered:

1. Any unplanned diary records will be mapped to planned visits by comparing the diary date against the dosing visits and assigned to the first visit that occurs after the unplanned diaries date.
2. If the subject has multiple diary records on the same date, then the below algorithm will be used to select the record for analysis:
  - a. Select 'DONE' records over 'NOT DONE'.
  - b. If one of the repeated records has 'NO Seizures' and the other is with some positive number as result, then select record with positive number of seizures.
  - c. If both/multiple repeated records have positive number of seizure, then include all seizures from both pages.

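### SAP 8.3.6 lists fewer other seizure types for the partial-onset cohort than SAP 6.2.3 and Appendix 1, and the only partial-onset frequency measure is one pooled rate

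*SAP*

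**What the plan says.** Both documents commit to a summary by type. Protocol 9.4: "Seizure frequency for each seizure type will be summarized using descriptive statistics every 4 weeks thereafter until the end of the study". SAP 8.3.6: "Seizure frequency for each seizure type will be summarized using descriptive statistics by visit until the end of the trial". (The two differ in schedule; that is not the point here.) Protocol 7.5 has the diary record "the seizure type for each seizure event", so the data exist by type.

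For frequency in the POS cohort, the SAP derives a single measure. SAP 6.2.3: "The 28-day seizure rate for all POS will be computed for subjects from Studies A0081042, A0081041, and direct enrollers". Appendix 1 of the SAP gives the same single rate. No section of the SAP defines a rate for simple partial, complex partial or secondarily generalised seizures, although Protocol 4.1 and 4.1.1 use those three classes to define the population.

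For seizures outside the rate, SAP 6.2.3 lists unclassified, status epilepticus, myoclonic, absence and tonic or tonic-clonic seizures. The number and percent of subjects with at least one "will be computed for all subjects for each visit in study A0081106 by primary seizure type cohorts (PGTC, POS"). Appendix 1 repeats the types and applies them to the POS and PGTC (primary generalised tonic-clonic) populations separately. The POS paragraph of SAP 8.3.6 instead speaks of types "not part of the 28-day POS rate (ie, unclassified, status epileptic").

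**The concern.** There are two linked problems.

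First, the SAP gives two different instructions for the same POS table. Section 8.3.6 is where an analyst would look for the specification of the seizure outputs, and its POS list is introduced by *ie*, which makes it a definition rather than a set of examples. Followed as written, it drops myoclonic, absence and tonic or tonic-clonic seizures. In children whose diagnosis is partial-onset epilepsy, those are the types that would show a new generalised seizure appearing on drug. Protocol 4.2 excludes absence seizures in directly enrolled subjects, so in that group an absence seizure on treatment would be either new or a missed exclusion. Either way it belongs in the summary.

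Second, a rate pooled over all partial seizures is dominated by whichever type is most frequent. A rise in the less frequent secondarily generalised seizures can be offset by a modest fall in the others. Because all seizure information is handled as safety (Protocol 9.2, SAP 6.1), the planned POS rate tables could show stable seizure control while the mix moved toward generalised convulsive seizures.

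**Working it through.** **Part 1: the lists side by side.** No arithmetic applies; the question is which types each section requires.

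| Type outside the 28-day rate | SAP 6.2.3, both cohorts | SAP Appendix 1, POS | SAP 8.3.6, PGTC | SAP 8.3.6, POS |
|---|---|---|---|---|
| Unclassified | yes | yes | yes | yes |
| Status epilepticus | yes | yes | yes | yes |
| Myoclonic | yes | yes | yes | no |
| Absence | yes | yes | yes | no |
| Tonic / tonic-clonic | yes | yes | yes | no |

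The punctuation of the tonic and clonic entry varies between sections, but the POS paragraph of 8.3.6 is the only place where the last three rows are absent. SAP 6.2.3 and Appendix 1 agree with each other, so this is a contradiction within the SAP and not a general omission. Even the fuller version gives subjects with at least one event, which shows emergence but not frequency.

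**Part 2: what the pooled POS rate can hide.** The plan states no figure to reproduce: there is no hypothesis test or power calculation, and the target of 100 paediatric completers does not bear on this.

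Inputs:
- The rate formula in SAP 6.2.3: seizures ÷ (days − missing diary days) × 28.
- The three partial classes in Protocol 4.1 and 4.1.1. I read the pooled rate as covering all three.
- The seizure mix, which the documents do not give. It is an assumption, shown over a range.

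One assumed subject over 28 days with no missing diary days: simple and complex partial go from 18 to 12, secondarily generalised from 2 to 6.
- Pooled rate before: (18 + 2) ÷ 28 × 28 = 20.
- Pooled rate after: (12 + 6) ÷ 28 × 28 = 18, a fall of 2 ÷ 20 = 10%.
- Secondarily generalised rate: 2 to 6, a tripling.

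In general, let *s* be the initial share of secondarily generalised seizures, *m* their multiplier and *r* the multiplier of the other partial types. The pooled rate changes by the factor *s·m* + (1 − *s*)·*r*. It is unchanged when *r* = (1 − *s·m*) ÷ (1 − *s*), so the fall in the other types that just hides the rise is 1 − *r*. For example, with *s* = 0.10 and *m* = 2: *r* = 0.80 ÷ 0.90 = 0.889, a fall of 11.1%.

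| Share *s* | Fall that hides a doubling | Fall that hides a tripling |
|---|---|---|
| 5% | 5.3% | 10.5% |
| 10% | 11.1% | 22.2% |
| 20% | 25.0% | 50.0% |
| 30% | 42.9% | 85.7% |

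The smaller the share, the easier it is to hide a rise. At 30% a large fall in the other types is needed, and the pooled rate is a better guide.

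**The case against.** **The other seizure types are planned.** From the POS paragraph of 8.3.6 alone, a reader might infer that the SAP does not summarise generalised seizures in POS children at all. The documents do not support that: 6.2.3 and Appendix 1 both require it. This objection stands in full, and the finding is one of inconsistency.

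**The commitment by type may mean only two types.** SAP 8.3.6 goes on to say "PGTC and POS seizure types will be summarized separately", so the SAP itself calls PGTC and POS seizure types, and Protocol section 9 allows the SAP to modify the plan. A reader might infer a broken promise of subtype rates; neither document promises rates for the three partial classes by name, so that is too strong. On the other side, Protocol 9.4 treats the PGTC/POS split as a separate subgroup factor: "Subgroup analysis will be done on the safety data and seizures rates for each age cohort and primary seizure type". If both phrases meant the same split, one would be redundant. The SAP's amendment history does not record that partial subtypes were set aside. The wording is ambiguous and needs a decision.

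**Severe seizures have other routes into the report.** Status epilepticus is counted for POS subjects under every version of the list. Worsening of the underlying disease counts as an adverse event (Protocol 8.3), and convulsions without hospitalisation are an example of an important medical event (Protocol 8.6). A reader might infer that a worsening could pass unseen in the whole study; that does not follow. What remains is that the diary-based POS rate would not show it, and adverse event tables give no 28-day rate by type.

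**Subtype rates would deliver limited information.** SAP 8.3.6 presents no POS baseline and gives its reasons; there is no concurrent control and no inference. Subtype rates would therefore show change between visits on treatment, not change from before treatment. The simple/complex distinction rests on impaired consciousness (Protocol Appendix 1) and may be less reliable in infants whose diaries are kept by parents. Both limits stand.

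**Conclusion.** The point holds in two parts, and it is minor.

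The contradiction between the POS paragraph of SAP 8.3.6 and SAP 6.2.3 with Appendix 1 is certain from the text. Three of the five entries required elsewhere are missing there, and an analyst following that paragraph would leave newly emergent generalised seizures in POS children out of the summary.

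The second part is a limitation of a descriptive choice. The sole POS frequency measure pools all partial seizures and can stay flat or fall while secondarily generalised seizures rise. At an assumed share of 5% to 20%, a fall of 5.3% to 25.0% in the other partial types is enough to hide a doubling. This shows what is possible, not what is likely, because the documents give no seizure mix. It also rests on reading the pooled rate as covering all three partial classes.

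**What to change.** 1. In SAP 8.3.6, make the POS list of other seizure types match 6.2.3 and Appendix 1: number and percent of POS subjects with at least one myoclonic, absence, tonic or tonic-clonic, unclassified or status epilepticus event, at each visit. Use one wording for the tonic and clonic entry in all three places.
2. State in 6.2.3 what a summary by seizure type covers. Beside the all-POS rate, add descriptive 28-day rates for simple partial, complex partial and secondarily generalised seizures, by visit and overall. If only one is added, it should be the secondarily generalised rate: it is the one most easily hidden and does not depend on the simple/complex distinction.
3. Note under the tables that, without a POS baseline, they show on-treatment change only.

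Cost: no new data collection and no inference. SAP 6.2.3 names seven visits plus overall, so three subtypes add 3 × 8 = 24 sets of descriptive statistics, each for the three treatment groups and combined.

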### **8.3.7. Laboratory, Vital Signs, Height, Weight, and ECG Data**

Laboratory, vital signs, height, weight and ECG data will be reported in accordance with the sponsor reporting standards for cohorts described in [Section 8](#) by treatment group and overall.

### **8.3.8. Physical and Neurological Examinations**

Physical and neurological examination data will be presented for cohorts described in [Section 8](#) by treatment group and overall.

### **8.3.9. Suicidal Ideation and Behavior**

#### C-CASA/C-SSRS

The denominator used in the percentages will be the number of subjects assessed for suicidal ideation and behavior (6 to 65 years of age).

The number and percent of subjects within each C-CASA category by treatment group and overall at baseline screening (lifetime) and at any time post-baseline without regard to baseline will be reported.

A subject listing of C-CASA categories as well as the underlying C-SSRS scale data will be presented.

#### CBCL

For the CBCL (4 to <6 years of age), the denominator used in the percentages will be the number of subjects assessed. Only subjects who fall within the age range for CBCL will be summarized. For subjects who falls outside of this age range and have CBCL data collected, CBCL data will only be displayed in the listing.

Additionally, some subjects <6 years are unable to have the CBCL administered due to translation issues (eg, Greek and Cebuano speaking subjects) and are administered the C-SSRS, which can be answered by the parents/caregivers. These children who have the C-SSRS administered will be displayed in listings only, ie, not summarized within the C-SSRS table.

A subject listing of CBCL scale data will be presented. Also, a summary table with the number and percent of subjects with a cut-off  $\geq 68$  on the T-scores for the Withdrawn, Internalizing Problems subscales and the Total Problem scales by treatment group at baseline screening (lifetime), and at any time post-baseline without regard to baseline will be reported.

C-CASA and CBCL will be presented combined for all subjects and subgroup summaries for each age cohort (for C-CASA only; see [Section 8](#)) and primary seizure type.

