#### **6.16. Visit 9 (Follow-up/End of Taper Visit-7 days Post-Completion/Discontinuation±3 Days)**

This visit is not required for subjects that do not enter the taper phase.

The following activities will be performed at Visit 9:

- Review and record adverse events.
- Review and record all concomitant medications and non-drug treatments/procedures.
- Collect and review seizure and dosing diary and record number and type of seizure.
- Collect urine sample for a urine pregnancy test (for female subjects who are menarchal).
- Evaluate and record study medication compliance.
- Complete assessment of suicidal ideation and behavior (C-SSRS or CBCL) using appropriate versions or test for subject's age. If CBCL is administered, scores must be obtained as soon as possible. If positive scores are obtained on the CBCL or CSSRS, a mental health risk assessment must be performed by a qualified mental health professional prior to randomization (please refer to [Section 7 - ASSESSMENTS](#)).

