### 7.6.1. Child Behavior Checklist (CBCL); Subjects 4 to <6 Years of Age

There are currently no validated scales to assess suicidal ideation and behavior in children below age 6, and suicidal ideation and behavior is an extremely rare occurrence in this age group. Children in this age group and young school-aged children are more likely to demonstrate aberrant behaviors that place them at-risk for self-injurious behaviors.

Therefore, the Child Behavior Checklist (CBCL) will be implemented to assess behaviors in young children that may place them at-risk for self-injury. The CBCL is a 100-item questionnaire designed to assess behavioral problems and social competency in children and has been used in studies of children with epilepsy. A parent or legally acceptable representative will complete the scale using pen and paper to rate the subject's problem behaviors and competencies. All items are rated on a 3-point scale (0 = Not true for that child; 1 = somewhat or sometimes true; and 2 = Very or often true) based on the subject's behavior in the past 2 months at Screening, and then since last visit at all other study visits (Visit 2-10). For this study, scores on the Withdrawn, Internalizing Problems subscales and the Total Problem scales will be obtained. Higher scores on the CBCL subscales indicate higher levels of problematic behaviors or dysfunction. The CBCL scoring algorithm allows for a subject's scores to be standardized using scores from a normal population. These standardized scores are referred to as T-scores. CBCL T-scores will be obtained utilizing a standardized computerized scoring system provided to the Sponsor by **CCI** [REDACTED]. For this study, a cut-off of  $\geq 68$  on the T-scores for the Withdrawn, Internalizing Problems subscales and the Total Problem scales will be used to determine whether a child is at-risk for SIB and requires a mental health risk assessment.

The CBCL will be used in this study for children who are 4-<6 years of age beginning at Visit 1. The CBCL will be completed at Visit 1 and for each subsequent visit through Visit 9 or Early Termination. The CBCL will be performed to assess for behavioral and emotional issues, including those that may be associated with suicidal ideation and behavior. See the [Schedule of Activities](#) for the visits at which the CBCL will be completed by a parent or legally acceptable representative.

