#### **6.2.4. Suicidal Ideation and Behavior (SIB) Assessments During the Clinical Trial**

*The correct age appropriate scale to assess suicidal ideation and behavior risk was used based on the guidance in the protocol, specifically the use of the Child Behavior Checklist (CBCL) for subjects <6 years of age) and the Columbia-Suicide Severity Rating Scale (C-SSRS) for subjects 6 - 65 years of age.*

C-SSRS responses will be mapped to the Columbia Classification Algorithm of Suicide Assessment (C-CASA). (see [Appendix 2](#)).

The following 3 endpoints are key endpoints for suicidal ideation and behavior data analysis and evaluation:

1. Suicidal Behavior.
2. Suicidal Ideation.

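### SAP 8.3.9 labels the CBCL baseline as lifetime and sets one baseline reading beside any of up to 7 or 8 later ones, so the post-baseline percentage is inflated without a drug effect; two key suicidality composites are also not specified there

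*SAP*

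**What the plan says.** **CBCL table.** SAP 8.3.9 plans "a summary table with the number and percent of subjects with a cut-off $\geq 68$ on the T-scores" for the Withdrawn, Internalizing Problems and Total Problem scales, "by treatment group at baseline screening (lifetime), and at any time post-baseline without regard to baseline will be reported". A listing of the CBCL data is planned as well. No by-visit, change or shift table is named.

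**CBCL recall.** Under Protocol 7.6.1 the parent's ratings are "based on the subject's behavior in the past 2 months at Screening, and then since last visit at all other study visits".

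**Number of readings.** Protocol 7.6.1 also says: "The CBCL will be completed at Visit 1 and for each subsequent visit through Visit 9 or Early Termination". Of Visit 9, Protocol 6.16 says: "This visit is not required for subjects that do not enter the taper phase". SAP Section 8 takes as baseline a single observation: the last before double-blind dosing in the earlier study, or Visit 1B for direct enrollers. All other data come from this study only.

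**C-CASA.** SAP 8.3.9 reports subjects within each C-CASA category "at baseline screening (lifetime) and at any time post-baseline without regard to baseline will be reported". SAP 6.2.4 states: "The following 3 endpoints are key endpoints for suicidal ideation and behavior data analysis and evaluation". The three are suicidal behavior (codes 1 to 3), suicidal ideation (code 4), and either of them.

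**The concern.** The CBCL paragraph uses almost the same phrase as the C-CASA paragraph. There, "lifetime" has a meaning, because the C-SSRS has a Lifetime version. The CBCL as used here has none.

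The layout also invites a before/after reading that it cannot bear. One column gives each child one chance to reach 68; the other gives up to 7 or 8 chances. A child who was at or above 68 before any drug counts in the second column exactly as a new case does. With no control arm, readers will naturally compare adjacent columns, and they could see behavioural worsening where nothing has changed.

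For the C-SSRS, a lifetime history stands beside about one year on study, and post-baseline events are not divided into first occurrences and recurrences. Two of the three endpoints that the SAP calls key, any behavior and behavior or ideation, have no table specified in 8.3.9.

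**Working it through.** **1. Label.** The SAP says lifetime. Protocol 7.6.1 sets two months at Screening and the interval since the last visit afterwards. These disagree, and no assumption is needed. The two-month window is documented only for Screening in A0081106. The window behind a rollover child's baseline is in the earlier study's protocol, which is not available here.

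**2. Number of readings.** Visits 2 to 8 give 7 post-baseline readings. Visit 9 makes 8, for children who taper. Early leavers have fewer. (Protocol 7.6.1 also mentions visits up to 10, but the schedule ends at Visit 9.)

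**3. Size of the inflation.** The plan states no figure to reproduce. The following model is assumed, with no drug effect: normal scores with the same distribution at every visit and equal correlation ρ between any two visits. Let p be the chance that one reading is at or above 68, c the matching standard-normal cut, U a standard normal variable, and k the number of post-baseline readings.

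q(U) = Φ((c − √ρ·U)/√(1−ρ))

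P(any of k at or above 68) = 1 − E[q(U)^k]

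The baseline column has expectation p. If T-scores had mean 50 and SD 10, c = (68 − 50)/10 = 1.8 and p = 3.6%; higher values of p allow for a clinical population. Results for k = 8, with the ratio to p in brackets:

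| p | ρ = 0.5 | ρ = 0.7 | ρ = 0.8 | ρ = 0.9 | ρ = 0.95 |
|---|---|---|---|---|---|
| 3.6% | 16.9% (4.7) | 12.9% (3.6) | 10.7% (3.0) | 8.2% (2.3) | 6.6% (1.8) |
| 10% | 36.7% (3.7) | 28.8% (2.9) | 24.5% (2.5) | 19.5% (2.0) | 16.4% (1.6) |
| 20% | 57.6% (2.9) | 47.1% (2.4) | 41.3% (2.1) | 34.3% (1.7) | 29.8% (1.5) |
| 30% | 71.8% (2.4) | 61.0% (2.0) | 54.7% (1.8) | 46.9% (1.6) | 41.7% (1.4) |

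Fewer readings give less. At p = 10% and ρ = 0.8 the ratio is 2.4 with 7 readings and 1.9 with 4. At p = 3.6% the limits with 8 readings are 1.0 at perfect correlation and, at independence, (1 − 0.964^8)/0.036 ≈ 7.1. If correlation instead decays with the distance between visits (first-order autoregressive, adjacent correlation 0.7 to 0.95), the ratio over the same values of p is 1.6 to 4.8.

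**4. New against pre-existing.** The chance of being below 68 at baseline and at or above 68 later is E[q(1 − q^k)]. At p = 10%, ρ = 0.8, k = 8, this is 15.4%. The other 24.5% − 15.4% = 9.1% were already at or above 68, so 9.1/24.5 = 37% of the children counted post-baseline are not new. One reading against one reading has an expected ratio of 1.0.

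**5. Composites.** SAP Appendix 2 maps separate C-SSRS answers to separate codes, so one subject can meet several. Suppose, as an illustration, that code 2 has 1 subject and code 4 has 2. Behavior or ideation is then 2 subjects if they overlap and 3 if they do not. The category counts do not say which.

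**The case against.** **The listings already separate new from old cases.** A reader might infer that new cases cannot be told from old ones at all. The documents do not support that: listings of the CBCL data, the C-CASA categories and the underlying C-SSRS data are planned, and in a small age group they are readable. What stands is that the summary table does not separate them, and for a study whose sole objective is safety and tolerability, sorting by hand is a poor substitute.

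**The size is not known.** A reader might take a doubling or tripling as established. It is only the middle of an assumed range; only the direction follows from the design.

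**Other evidence exists.** It is tempting to call the before/after contrast the only evidence on these risks. It is not: adverse events are collected throughout, and a positive C-SSRS or a CBCL score at or above 68 calls for a mental health risk assessment (Protocol 7.6.5).

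**An inclusive safety count is defensible.** Counting every post-baseline event regardless of history is a legitimate choice, and the column says that it does so. A reader might infer that the lifetime column hides new-onset ideation. It does not reduce the post-baseline count; it only leaves new onset undivided from recurrence.

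**The composites may still be produced.** Section 8.3.9 does not exclude them, and ideation is code 4, so one of the three is covered. If each subject were counted once, in the most severe category, the counts could be added; the SAP states no such rule. The fair statement is that 8.3.9 does not specify the two composites, not that they will be missing.

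**Conclusion.** The point holds in limited form. Three parts rest on the text alone: the lifetime label is wrong for the CBCL; the two columns rest on different numbers of readings; and 8.3.9 specifies no table for two of the three endpoints that 6.2.4 calls key.

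The upward direction needs only that the rate at a single visit is unchanged and that readings are not perfectly correlated. The size, about 1.4- to 4.7-fold with 8 readings, rests on assumed rates (3.6% to 30%), assumed equal correlations (0.5 to 0.95) and normal scores; the documents supply none of these. It will be smaller for children with fewer readings. Two features are not modelled: recall windows differ between Screening and later visits, and children at or above 68 at Screening may not be enrolled, which could lower the baseline column and widen the gap.

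SAP 4.1 plans no formal analysis, so no test or error rate is affected. The risk is misreading of a descriptive safety table. It is worth correcting because the remedy uses data already collected.

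**What to change.** In SAP 8.3.9:

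- **(a)** Delete the lifetime label for the CBCL and state the actual recall window: two months at Screening in A0081106 and, for rollover subjects, whatever window the earlier study used.
- **(b)** Report n (%) with T-score at or above 68 at baseline and at each visit, for each of the three scales. Keep the any-time count as a supplement.
- **(c)** Add a shift table of baseline (below 68, at or above 68) by worst post-baseline reading, optionally also by last reading. The last reading alone would miss a child who rises mid-study and then falls.
- **(d)** Tabulate the three endpoints of SAP 6.2.4 at subject level, and split post-baseline C-CASA events by lifetime history into new onset and recurrence.

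The cost is SAP wording and a few short descriptive tables; no new data are needed. Cells will be small in the 4 to <6 year group, so show counts beside percentages.
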